12.1.5 Exploratory Analyses

Table 117: Moderator: MINI AUD (Percent Heavy Drinking Days Weeks 3-12)

Type III Wald Tests

Parameter	Num DF	Den DF	F Value	p-value
ARM	1	XXX	XXX.XX	0.xxx
Week	11	XXX	XXX.XX	0.xxx
Site	9	XXX	XXX.XX	0.xxx
Baseline MINI AUD	1	XXX	XXX.XX	0.xxx
ARM*MINI AUD	1	XXX	XXX.XX	0.xxx

Least Squares Means

	Louis Se uni es ivients											
					95% CI							
AUD Split	Arm	Week	Estimate	SE	Lower CI	Upper CI	Difference	SE	p-value	Cohen's d		
Yes	Oxytocin	Overall	XX.XX	0.xxx	0.xxx	0.xxx	X.XXX	X.XXX	0.xxx	xx.xxx		
	Placebo	Overall	XX.XX	0.xxx	0.xxx	0.xxx						
No	Oxytocin	Overall	XX.XX	0.xxx	0.xxx	0.xxx	X.XXX	X.XXX	0.xxx	xx.xxx		
	Placebo	Overall	XX.XX	0.xxx	0.xxx	0.xxx						

Table 118: Moderator: POMS Tension-Anxiety (Percent Heavy Drinking Days Weeks 3-12)

Shell style similar to Table 117

Table 119: Moderator: POMS Depression-Dejection (Percent Heavy Drinking Days Weeks 3-12)

Shell style similar to Table 117

Table 120: Moderator: ECR-RS Attachment-Related Anxiety (Percent Heavy Drinking Days Weeks 3-12)

Shell style similar to Table 117

Table 121: Moderator: STAI (Percent Heavy Drinking Days Weeks 3-12)

Shell style similar to Table 117

Table 122: Moderator: Drinking Goal (Percent Heavy Drinking Days Weeks 3-12)

Shell style similar to Table 117

Table 123: Moderator: BIS Self Control (Percent Heavy Drinking Days Weeks 3-12)

Shell style similar to Table 117

Table 124: Moderator: BIS Impulsive Behavior (Percent Heavy Drinking Days Weeks 3-12)

Shell style similar to Table 117

Table 125: Moderator: Hyperkatifeia (Percent Heavy Drinking Days Weeks 3-12)

Shell style similar to Table 117

 Table 126:
 Hyperkatifeia Total Score

		Oxytocin						Placebo					
Study Week	N	Mean	SD	Median	Min	Max	N	Mean	SD	Median	Min	Max	
Baseline	XX	XXX	XXX	XXX	XXX	XXX	XXX	XXX	XXX	XXX	XXX	XXX	
13	XX	XXX	XXX	XXX	XXX	XXX	XXX	XXX	XXX	XXX	XXX	XXX	

Table 127: Hyperkatifeia Total Score- Generalized Linear Model, Week 13

Type III Wald Tests

Parameter	Num DF	Den DF	F Value	p-value
ARM	1	XXX	XXX.XX	0.xxx
Site	9	XXX	XXX.XX	0.xxx
Hyperkatifeia	1	XXX	XXX.XX	0.xxx

Least Squares Means

100

			95% CI				Untransformed		Transformed	
Arm	Estimate	SE	Lower CI	Upper CI	Difference	SE	p-value	Cohen's d	p-value	Cohen's d
Oxytocin	XX.XX	0.xxx	0.xxx	0.xxx	X.XXX	X.XXX	0.xxx	xx.xxx	0.xxx	XX.XXX
Placebo	XX.XX	0.xxx	0.xxx	0.xxx						

Table 128: Hyperkatifeia Stress/Anxiety Score

Same as Table 126

Table 129: Hyperkatifeia Stress/Anxiety Score- Generalized Linear Model, Week 13

Same as Table 127

Table 130: Hyperkatifeia Depression Score

Same as Table 126

Table 131: Hyperkatifeia Depression Score- Generalized Linear Model, Week 13

Same as Table 127

Table 132: Hyperkatifeia Irritable Score

Same as Table 126

Table 133: Hyperkatifeia Irritable Score- Generalized Linear Model, Week 13

Same as Table 127

Table 134: Hyperkatifeia Pain Score

Same as Table 126

Table 135: Hyperkatifeia Pain Score- Generalized Linear Model, Week 13

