7.0 SAMPLE SIZE CONSIDERATIONS

With an intake sample of 100 subjects (50 subjects per arm) and 12% attrition, it is projected that the sample size for primary endpoint analyses will be 88 (44 subjects per arm). The alpha level for the primary analyses will be 0.05, two-tailed. An estimate of the effect size (Cohen's d) for the investigational products is 0.60. Equal variances in both groups are assumed. These assumptions lead to a projected power of 0.80.

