9.0 STATISTICAL CONSIDERATIONS

9.1 General Considerations

For descriptive purposes, dichotomous and categorical variables will be presented as number of observations and percentages; continuous variables will be given as means, standard deviations (SD), median, minimum (min) and maximum (max). Statistical tests will be two-tailed at a 0.05 Type I error rate. P-values for the primary and secondary endpoints of < 0.05 will be considered statistically significant. Endpoint data will also be screened for outliers and skewness. Appropriate non-parametric tests will be used to compare treatment groups on continuous baseline characteristics that are not normally distributed. Continuous endpoint data that are not normally distributed will be transformed using either a square root, logarithmic, or inverse transformation, the selection of which is determined by skewness and kurtosis statistics with values closest to zero and normalization of histograms. Cohen's d will be used to calculate the effect size for means. Odds ratios will be provided for all dichotomous outcomes. Descriptive statistics – mean, SD, median, min and max – of all endpoint data will be provided for each assessment point or summarized at each week for drinking endpoints. All data will be presented in listings. All analyses will be performed in the full analysis set.

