9.11 Exploratory Analyses

A number of variables will be tested as potential moderators of the medication treatment effect on the PHDD primary endpoint. Weeks 3-12 will be the period of interest. The model identified in Section 9.4.1 will be amended to include the potential moderator variable and the moderator by treatment group interaction. To aid with interpretation, continuous moderator variables will be dichotomized based on clinically accepted levels available from the literature. In the event a clinically meaningful cutoff is not available, LOESS curves will be used to identify a cut point. The LOESS curve analysis will use averaged PHDD data over study weeks 3-12, treatment group and the moderator of interest. In all approaches, an appropriate cutoff will be one that ensures a sufficient sample size in all resultant subgroups. The potential moderator variables are assessed at baseline and include: sex, IDS-30 reward/relief drinking, baseline drinks per week, measures of anxiety and depression (ECR-RS anxiety-related attachment, POMS subscales of depression and anxiety, Spielberger Trait Anxiety Inventory), Barratt Impulsiveness Scale, history of alcohol withdrawal (i.e., withdrawal question on the MINI for alcohol use disorder), and alcohol-related treatment goal.

There is interest in exploring the use of a new Hyperkatifeia Scale as an efficacy endpoint and moderator of drug response. Hyperkatifeia scores are assessed at Week 1 and Week 13 (EOS Visit 9). Exploratory analyses utilizing Hyperkatifeia Scale scores will include: 1) using the total score and subscales as an endpoints to assess treatment efficacy; and 2) conducting moderator analyses using total score and the subscales. The total score and subscales are the sum of the items.

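### The moderator tables give each subgroup its own treatment p-value without tying it to the interaction, and show no interaction estimate, so a uniform effect near d = 0.60 would look confined to one subgroup for about half the moderators

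*SAP*

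**What the plan says.** SAP 9.11 sets out the moderator analyses of percent heavy drinking days over Weeks 3-12: "The model identified in Section 9.4.1 will be amended to include the potential moderator variable and the moderator by treatment group interaction". Moderators measured on a continuous scale are split in two, at a literature cutoff or, where none exists, at a cut point read from LOESS curves.

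SAP 12.1.5 gives the output. Table 117 is headed "Moderator: MINI AUD (Percent Heavy Drinking Days Weeks 3-12", and Tables 118-125 reuse its format, so nine moderator tables are laid out. Each has two blocks:

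- A Type III block, in which the treatment-by-moderator row carries degrees of freedom, an F value and a p-value.
- A least-squares-means block, in which each moderator level has arm means with 95% CIs, then the oxytocin-placebo difference with its SE, p-value and Cohen's d.

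The CI columns belong to the arm means. No CI is laid out for either subgroup difference, and neither an estimate nor a CI for the difference between the two subgroup effects.

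SAP 9.11, Protocol 11.4.7 and the shells do not make the subgroup p-values depend on the interaction, or say how to read one significant and one non-significant subgroup. The threshold that reaches these tests is the general one in SAP 9.1: "Statistical tests will be two-tailed at a 0.05 Type I error rate". Both documents label the analyses exploratory.

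**The concern.** The moderator analyses are there to show whether some patients respond better than others. That is a question about the difference between two subgroup effects. The shell tests that difference but does not estimate it, and the most detailed rows in the table answer another question: whether the drug beats placebo within each half of the sample.

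Half of a trial that was sized for its overall effect has roughly a coin-flip chance of significance. One subgroup below 0.05 and the other above it is therefore an ordinary result when everyone responds alike. A reader who contrasts the two p-values would report a responder group that does not exist, and a later trial might be restricted to it.

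**Working it through.** **Inputs.** SAP 7.0 plans for 100 randomised (50 in each arm), 12% lost, and so 88 analysed (44 in each arm). On the effect it says "An estimate of the effect size (Cohen's d) for the investigational products is 0.60". On the significance level it says "The alpha level for the primary analyses will be 0.05, two-tailed". Equal variances are stated there, so SD = 1 on the d scale. The documents do not give the share of patients in each subgroup. I assume 50:50 and show the range to 80:20. The outcome is treated as one mean per subject, as the SAP's own power statement does, and the splits as unrelated to outcome.

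**The plan's own figure.** Normal approximation: power = Φ(d√(n/2) − 1.960).
- n = 44 per arm: 0.60 × √22 = 2.814; Φ(2.814 − 1.960) = Φ(0.854) = 0.80. The noncentral t gives 0.795. The stated 0.80 is reproduced.
- Attrition: 44 / 0.88 = 50 per arm, as stated.

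**Power in one half.** n = 22 per arm: 0.60 × √11 = 1.990; Φ(1.990 − 1.960) = Φ(0.030) = 0.51. With t it is 0.49 (42 df) or 0.50 (pooled error df).

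**Chance that exactly one subgroup is significant, no true moderation.** The subgroups share no patients, so P = p1(1 − p2) + p2(1 − p1). At 50:50 and d = 0.60 this is 2 × 0.503 × 0.497 = 0.50. Both are significant with probability 0.25, and neither with probability 0.25.

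| Split (44 per arm, d = 0.60) | Power, larger / smaller subgroup | Exactly one significant |
|---|---|---|
| 50:50 | 0.503 / 0.503 | 0.50 |
| 60:40 | 0.577 / 0.421 | 0.51 |
| 70:30 | 0.643 / 0.332 | 0.55 |
| 80:20 | 0.701 / 0.238 | 0.61 |

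| True uniform d (50:50 split) | Exactly one significant |
|---|---|
| 0.8 | 0.38 |
| 0.6 | 0.50 |
| 0.5 | 0.47 |
| 0.4 | 0.38 |
| 0.3 | 0.28 |
| 0.2 | 0.18 |
| 0 | 0.095 |

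With all 50 per arm analysed and d = 0.60, the range over splits is 0.49 to 0.62.

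**How often the interaction disagrees.** A simulation of 20,000 trials (d = 0.60, random 50:50 moderator, pooled error variance, no true interaction) gives exactly one significant subgroup in 0.49 of trials. In 0.44 to 0.45 of trials it occurs with a non-significant interaction, and in about 0.05 with a significant one. Among trials with a significant overall effect, the 0.49 becomes 0.57.

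**Across the nine tables.** The expected number of discordant tables is 9 × 0.50 = 4.5. If a one-subgroup reading is allowed only when the interaction is significant, it is 9 × 0.05 = 0.45. These are expected counts. The moderators are measured on the same patients and are likely correlated, so the count in one trial can lie well away from 4.5.

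**The case against.** The correct test is planned and printed. SAP 9.11 names the interaction, and its p-value stands above the subgroup rows in the same table. The estimate will also exist: SAP 9.4.1 requests the fixed-effects solution, and because 9.11 adds no three-way term, the interaction coefficient for a two-level moderator is the difference between the subgroup effects. The analyses are exploratory, Protocol 11.4.11 calls the trial a pilot, and neither document makes a subgroup claim. All of this stands. It makes this a fault of reporting and interpretation, not of the model. The subgroup tests nevertheless remain unlinked to the interaction, and the quantity under study has no place in the table.

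Three stronger readings are tempting, and the documents do not support them.

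- *The tables would produce spurious responders if oxytocin does nothing.* With 16 moderators (a count of the SAP 9.11 list) and d = 0, simulation gives at least one subgroup p < 0.05 in 0.47 to 0.49 of trials, but at least one interaction p < 0.05 in 0.46 to 0.54. Unadjusted interaction tests give false positives about as often, so this is no argument for changing the tables.
- *The full SAP 9.11 list will be printed, with more than 30 subgroup p-values.* Only nine tables are laid out, which makes 18. Sex, the IDS-30 scores, baseline drinks per week and the Hyperkatifeia subscales have no moderator shell.
- *SAP 9.1 declares these subgroup results significant.* Its sentence "P-values for the primary and secondary endpoints of < 0.05 will be considered statistically significant" names primary and secondary endpoints and does not mention exploratory moderator tests. Only the general 0.05 rule reaches them.

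It is also true that deleting p-values does not prevent the misreading if subgroup CIs remain, because one CI excluding zero and the other not is the same discordance. The interpretive sentence is therefore an essential part of the change.

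**Conclusion.** The point holds as one about what the moderator tables display and how they are to be read. SAP 9.11 chooses the right test, but the shells for Tables 117-125 omit its estimate and CI, while giving within-subgroup p-values and effect sizes that nothing ties to it.

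For a uniform effect at the planning value, about half the moderators would show exactly one significant subgroup, nearly always with a non-significant interaction. That figure rests on a true d near 0.60, 44 analysed per arm, splits near 50:50 and one mean per subject. It is much lower for small effects and higher for uneven splits. Cut points chosen from LOESS curves of the outcome are not allowed for.

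The primary analysis is unaffected. What is at risk is the trial's answer to the question of who responds, and the correction is cheap enough to be worth making.

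**What to change.** In the Table 117 shell, and so in Tables 118-125:

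1. Add one row for the interaction estimate (the difference between the two subgroup effects) with its 95% CI and p-value, as the test of moderation.
2. Remove the within-subgroup p-values.
3. Keep the subgroup differences, add their 95% CIs, and label them as descriptive.

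In SAP 9.11, add two sentences: that moderation is judged only by the interaction, never by one subgroup being significant (or its CI excluding zero) while the other is not; and that the interaction p-values are exploratory and unadjusted for the number of moderators examined.

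The model, data and primary analysis do not change. The work is two sentences and one shell. The small loss is that subgroup p-values are no longer shown.

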12.2 Listings

Listing 1: Subject Disposition - All Subjects

Subject ID	Date of Consent	Treatment Group	Full Analysis Set	Study Completi on	(Day) Date of Study Completion or Early Discontinuation	Reason for Early Discontinuation	Subject confined or incar- cerated	Start Date/ End Date of confinement
xxx	mm/dd/yyyy	Oxytocin	Yes	Yes	(xx) mm/dd/yyyy	xxxxxx	Yes	mm/dd/yyyy / mm/dd/yyyy
		Placebo	No	No			No	
		None						

Note: Day is relative to Study Day 0.

Listing 2: Enrollment and Randomization – All Consented Subjects

Subject ID	Treatment Group	Date of Consent	Did the subject meet all eligibility criteria?	Randomized?	Date of Randomization	Kit Number
XXX	Oxytocin	mm/dd/yyyy	Yes	Yes	mm/dd/yyyy	XXX
	Placebo		No	No		

103

Listing 3: Reason not Eligible – Screen Failures

Subject ID	Criterion Type	Criterion
XXX	Inclusion Criteria	
	Exclusion Criteria	

Listing 4: Protocol Deviations

Subject ID	Treatment Group	Deviation Date	Protocol Deviation	Details
XXX	Oxytocin	mm/dd/yyyy	Subject Failed to Meet the Inclusion/Exclusion Criteria	
XXX	Placebo	mm/dd/yyyy	Source Documentation was Not Available	
			Pregnancy Test Not Performed	
			Required study data was not obtained or obtained late due to site error	
			Informed Consent Deviation	
			AE/SAE Reporting Deviation	
			Other Deviation:	xxxxxxxxxxxx

104

Note: Only subjects with protocol deviation are listed.

Listing 5: Subjects Excluded from the Efficacy Analysis

Subject ID	Treatment Group	Reason for Exclusion from FA
Xxx	Overtagin	
AXX	Oxytocin Placebo	XXXXXX

Note: Only subjects excluded from the efficacy analysis are listed.

Listing 6: Demographics Data

Subject ID	Treatment Group	Gender	Age (yrs)	Ethnicity	Race	Marital Status
XXX	Oxytocin	Male	XX	Hispanic or Latino	American Indian or Alaska Native	Married
				Not Hispanic or		
	Placebo	Female		Latino	Asian	Divorced
				Unknown	Native Hawaiian or Other Pacific Islander	Living with Partner
					Black or African American	Widowed
					White	Separated
					Other	Never Married
					Unknown	Unknown
						Missing

Subject ID	Treatment Group	Years of Education	Years of Formal Education (GED=12years)	Usual Employment Pattern in the last 30 days
XXX	Oxytocin	XX	XXX	Full-time, 35+ hrs/week
	Placebo			Part-time, regular hours
				Part-time, irregular
				hours/daywork
				Student
				Military service
				Unemployed
				Retired/Disabled
				Homemaker
				In controlled environment
				Unknown
				Unknown

Listing 7: Baseline Drinking Characteristics

Subject	Treatment	Drinks/Week	Drinks/Week (Days -1 to -7 Pre-	% Change Drinks per Week Pre- screen to Pre-	Drinks/ Drinking Day	Drinks/Drinking Day (Days -1 to - 7 Pre-	% Change DPDD Pre- screen to Pre-
ID °	Group	(Days -1 to -28)	randomization)	randomization	(Days -1 to -28)	randomization)	randomization
XXX	Oxytocin	XXX.X	XXX.X	XX.X	XXX.X	XXX.X	XX.X
	Placebo		_				

Subject ID	Treatment Group	Weekly % Heavy Drinking Days (Days -1 to -28)	Weekly % Days Abstinent (Days -1 to -28)	WHO Risk Level
XXX	Oxytocin	XXX.X	XXX.X	High Risk
	Placebo			Very High Risk

Listing 8: MINI DSM5 Disorders

Subject ID	Treatment Group	Visit Date	Diagnosis	Timeframe
XXX	Oxytocin	mm/dd/yyyy	xxxxxx	Current (2 weeks)
	Placebo			Past
				Recurrent

Note: Only subjects with a diagnosis of a disorder will be listed.

Listing 9: MINI DSM5 AUD

Subject ID	Treatment Group	Visit Date	# of Symptoms
VVV	Oxytocin	mm/dd/yyyy	VV
XXX	Placebo	mm/dd/yyyy	XX

Listing 10: MINI AUD End of Study

Subject ID	Treatment Group						Item						# of Symptoms
		1	2	3	4	5	6	7	8	9	10	11	
XXX	Oxytocin	Y	Y	Y	Y	Y	Y	Y	Y	Y	Y	Y	
	Placebo	N	N	N	N	N	N	N	N	N	N	N	
		NA	NA	NA	NA	NA	NA	NA	NA	NA	NA	NA	

Item #	List of Items
1	a. During the times when you drank alcohol, did you end up drinking more than you planned when you started?
2	b. Did you repeatedly want to reduce or control your alcohol use? Did you try to cut down or control your alcohol use, but failed? IF YES TO EITHER, MARK YES.
3	c. On the days that you drank, did you spend substantial time obtaining alcohol, drinking, or recovering from the effects of alcohol?
4	d. Did you crave or have a strong desire or urge to use alcohol?
5	e. Did you spend less time meeting your responsibilities at work, at school, or at home, because of your repeated drinking?
6	f. If your drinking caused problems with your family or other people, did you still keep on drinking?
7	g. Were you intoxicated more than once in any situation where you or others were physically at risk, for example, driving a car, riding a motorbike, using machinery, boating, etc.?
8	h. Did you continue to use alcohol, even though it was clear that the alcohol had caused or worsened psychological or physical problems?
9	i. Did you reduce or give up important work, social or recreational activities because of your drinking?
10	j. Did you need to drink a lot more in order to get the same effect that you got when you first started drinking or did you get much less effect with continued use of the same amount?
11	K1. When you cut down on heavy or prolonged drinking did you have any of the following: [increased sweating or heart rate; hand tremor or "the shakes"; trouble sleeping; nausea or vomiting; hearing or seeing things other people could not see or hear or having sensations in your skin for no apparent reason; agitation; anxiety; seizures] (If yes to 2 or more of these, check yes for this question), OR K2. Did you drink alcohol to reduce or avoid withdrawal symptoms or to avoid being hung over? If K1 or K2 = yes, then score as yes.

Listing 11: Medical History

Subject ID No.	Treatment Group	SOC	Specify (Preferred Term/ Verbatim Term)	Start Date	Ongoing
	•				8 8
		Blood and Lymphatic System			
XXX	Oxytocin	Disorders	Xxxxxxxxxx/ xxxxxxxx	mm/dd/yyyy	No
	Placebo	Cardiac Disorders			Yes
		Congenital, Familial and Genetic Disorders			
		Ear and Labyrinth Disorders			
		Endocrine Disorders			
		Eye Disorders			
		Gastrointestinal Disorders			
		General Disorders and Administration Site Conditions			
		Hepatobiliary Disorders			
		Immune System Disorders			
		Infections and Infestations			
		Injury, Poisoning and Procedural Complications			
		Investigations			
		Metabolism and Nutrition Disorders			
		Musculoskeletal and Connective Tissue Disorders			
		Neoplasms Benign, Malignant and Unspecified (incl Cysts and Polyps)			
		Nervous system Disorders			
		Pregnancy, Puerperium and Perinatal Conditions			
		Psychiatric Disorders			

Renal and Urinary Disorders
Reproductive System and Breast
Disorders
Respiratory, Thoracic and
Mediastinal Disorders
Skin and Subcutaneous Tissue
Disorders
Social Circumstances
Surgical and Medical Procedures
Vascular Disorders
Other:xxxxxxxx

Listing 12: Surgical History

Subject ID No.	Treatment Group	Has the subject had any past surgeries?	Date of Surgery	Type of Surgery
XXX	Oxytocin	Yes	mm/dd/yyyy	XXXXXXXXXXX
	Placebo	No		

Listing 13: Physical Exam

Subject ID No.	Treatment Group	Exam Date		Any abnormal finding during the physical exam?	Describe
XXX	Oxytocin	mm/dd/yyyy		Yes	XXXXXXX
	Placebo			No	

Programming Note: Only report the items that are abnormal

Listing 14: Drinking Treatment History

Subject ID No.	Treatment Group	Age first started drinking alcohol regularly	Number of lifetime inpatient visits to get help with reducing or quitting drinking	Number of lifetime inpatient hospitalizations for illnesses, injuries, or accidents due to drinking	Number of times in lifetime underwent alcohol detoxification using medication	Number of lifetime outpatient visits with a health professional to get help with reducing or quitting drinking	Number of group meetings attended for alcohol problems or drinking in the past year
XXX	Oxytocin	XXX	XXX	XXX	XXX	XXX	XXX
	Placebo						

Listing 15: Drinking Goal

				Subjects wanting to reduce drinking, expected drinks per day								
Subject ID	Treatment Group	Visit Date	Which treatment goal would you like to achieve by the end of the study?		Tues	Wed	Thur	Fri	Sat	Sun		
XXX	Oxytocin	mm/dd/yyyy	Abstinence	X	X	X	X	X	X	х		
	Placebo		Reduction but not stop									

Subject ID	Treatment Group	Visit Date	How motivated to reach your goal?	How confident to achieve your goal?
XXX	Oxytocin	mm/dd/yyyy	1=Not Motivated	1=Not Confident
	Placebo		2, 3, 4, 5, 6, 7, 8, 9	2, 3, 4, 5, 6, 7, 8, 9
			10=Extremely Motivated	10=Extremely Confident
			Refuse to answer	Refuse to answer

Listing 16: Daily and Weekly Standard Drink Units (TLFB) During Treatment

Subject ID	Treatment Group	Week	D1	D2	D3	D 4	D5	D6	D7	Mean drinks/day	Mean drinks/ drinking day	Heavy drinking days	% days abstinent
XXX	Oxytocin	1	XX	XX	XX	XX	XX	XX	XX	XX.XX	XX.XX	XX.XX	XX
	Placebo	2											
		3, etc											

Listing 17: Drinking Question

Subject ID	Treatment Group	Date of Assessment	Did the subject have any drinking days since the last visit?	Did the subject have any heavy drinking days since the last visit?	Date of last visit
XXX	Oxytocin	mm/dd/yyyy	Yes	Yes	mm/dd/yyyy
	Placebo		No	No	
•					

Listing 18: Drinking Consequences, Craving, Appetite, and Anxiety

Subject ID	Treatment Group	Week	Urge to Drink	CIWA-AR	STAI	SNAQ	ECR-RS Attachment- Related Anxiety	BIS Total Score
XXX	Oxytocin	XX		XX	XX	XX	XX	XX
	Placebo							

Listing 19: UPSIT Scores

Subject ID	Treatment Group	Week	Total Score	Category
XXX	Oxytocin	XX	XX	Normosmia
	Placebo			Mild microsmia
				Moderate microsmia
				Severe microsmia
				Anosmia
				Normosmia

Listing 20: POMS Scores

Subject ID		Week	Scores								
	Treatment Group		Total Mood Disturbance	Tension	Depression	Anger	Fatigue	Confusion	Vigor		
XXX	Oxytocin	XX	XXX	XXX	XXX	XXX	XXX	XXX	XXX		
	Placebo										

Listing 21: PROMIS Scale Scores

Subject ID	Treatment Group	Week	Sleep Disturbance	Alcohol Negative Consequences	Pain Interference
XXX	Oxytocin	XX	XX	xx	XX
	Placebo				

Listing 22: Smoking Data

Subject ID	Treatment Group	Week	Visit Date	Over the past week, how many days did you smoke cigarettes?	On the days you smoked, how many cigarettes did you smoke on average?	How many days did you use other tobacco or nicotine products during the past week?
XXX	Oxytocin	1, 6, 8, 10, 13	mm/dd/yyyy	x	XX	X
	Placebo	1, 0, 0, 10, 13				

Listing 23: Exit Interview

Subject ID	Treatment Group	Visit Date	What study drug do you believe you were taking?	Why do you think you received that drug?	Do you feel the study drug helped you to reduced drinking?	How would you describe your experience taking the study drug?
xxx	Oxytocin	mm/dd/yyyy	Placebo	Had side effects	Very Much	Experienced no unwanted side effects and benefited from taking the medication
	Placebo		Active medication	Had no side effects	Much	Experienced some unwanted side effects but benefited from taking the medication
			Both placebo and active	Staff told me	Moderately	Experienced a lot unwanted side effects but benefited from taking the medication
			Don't know	Staff treatment me different	A Little	Experienced no unwanted side effects but did not benefit from taking the medication
			Other substance	No improvement in drinking	Not Little	Experienced some unwanted side effects and did not benefit from taking the medication
				Had improvement in drinking	Not at all	Experienced a lot of unwanted side effects and did not benefit from taking the medication
				Had a hunch		
				I just felt different		
				Other: xxxxx		

Subject ID	Treatment Group	Visit Date	If a friend were in need of help for a drinking problem, would you recommend taking the study drug to him/her?	If you were to need treatment in the future, would you choose to take the study drug again?	How much do you think of yourself as wanting to please other people (people pleaser)?
XXX	Oxytocin	mm/dd/yyyy	Yes, definitely	Definitely yes	More than average
	Placebo		Yes, generally	Probably yes	Average
			Neither yes nor no	Maybe	Less than average
			No, not really	Probably not	
			No, definitely not	Definitely not	

Listing 24: Other Services Use

Subject ID	Group	Date	Week	Since your last visit did you attend any AA, 12-step, SOS, or similar group meeting?	How many?	Have you visited another health professional to get help reducing drinking?	What type of professional?
XXX	Oxytocin Placebo	mm/dd/yyyy	XX	Yes No	XXXX	Yes No	XXXXX

Listing 25: Drug Exposure

Subject ID No.	Treatment Group	Study Month	Date Start of Month	Date End of End of Month	Volume of Drug Prescribed	Volume of Drug Taken	Reason for Discontinuation
XXX	Oxytocin	1, 2, 3	mm/dd/yyyy	mm/dd/yyyy	xx	XX	
	Placebo						

Listing 26: Adverse Events

Subject ID	Treatment Group	Adverse Event (Verbatim) S: SOC P: PT Term	Start Date/ Day	Stop Date/ Day	Duration in Days	Severity	Relation -ship	Actions Taken	Outcome	Serious
XXX	Oxytocin	Verbatim	mm/dd/yyyy	mm/dd/yyyy		1	1	1	1	Yes
	Placebo	S: xxxx	XX	XX		2	2	2	2	No
		P: xxxx				3	3	3	3	
						4	4	4	4	
							5	5	5	
								6		

Severity: 1=Mild; 2=Moderate; 3=Severe; 4=Potentially Life-threatening. Relationship: 1= Unrelated; 2=Unlikely; 3=Possibly; 4=Probably; 5=Definitely

Action Taken Due to AE: 1=None; 2=Treated with Drugs; 3=Non-drug treatment; 4=ER/Outpatient visit; 5=Hospitalization; 6=Referral for treatment

Outcome: 1=Resolved; 2=Recovered with sequelae; 3=Ongoing; 4=Required treatment; 5=Unknown

Programmer's Note: If "Were any AEs reported?" checkbox=No, then display "None Reported" in the Adverse Event column and SOC/PT column. If an AE started and stopped the same day, the duration is 1 day.

Listing 27: Adverse Events Leading to Subject Discontinuation from Study

Subject ID	Treatment Group	Adverse Event (Verbatim) S: SOC P: PT Term	Start Date/ Day	Stop Date/ Day	Duration in Days	Severity	Relation -ship	Actions Taken	Outcome	Serious
XXX	Oxytocin	Verbatim	mm/dd/yyyy	mm/dd/yyyy		1	1	1	1	Yes
	Placebo	S: xxxx	XX	XX		2	2	2	2	No
		P: xxxx				3	3	3	3	
						4	4	4	4	
							5	5	5	
								6		

Severity: 1=Mild; 2=Moderate; 3=Severe; 4=Potentially Life-threatening. Relationship: 1= Unrelated; 2=Unlikely; 3=Possibly; 4=Probably; 5=Definitely

Action Taken Due to AE: 1=None; 2=Treated with Drugs; 3=Non-drug treatment; 4=ER/Outpatient visit; 5=Hospitalization; 6=Referral for treatment

Outcome: 1=Resolved; 2=Recovered with sequelae; 3=Ongoing; 4=Required treatment; 5=Unknown

Programmer's Note: If "Were any AEs reported?" checkbox=No, then display "None Reported" in the Adverse Event column and SOC/PT column. If an AE started and stopped the same day, the duration is 1 day.

Listing 28: Adverse Events Leading to Discontinuation of Investigational Product

Subject ID	Treatment Group	Adverse Event (Verbatim) S: SOC P: PT Term	Start Date/ Day	Stop Date/ Day	Duration in Days	Severity	Relation -ship	Actions Taken	Outcome	Serious
XXX	Oxytocin	Verbatim	mm/dd/yyyy	mm/dd/yyyy		1	1	1	1	Yes
	Placebo	S: xxxx	XX	XX		2	2	2	2	No
		P: xxxx				3	3	3	3	
						4	4	4	4	
							5	5	5	
								6		

Severity: 1=Mild; 2=Moderate; 3=Severe; 4=Potentially Life-threatening. Relationship: 1= Unrelated; 2=Unlikely; 3=Possibly; 4=Probably; 5=Definitely

Action Taken Due to AE: 1=None; 2=Treated with Drugs; 3=Non-drug treatment; 4=ER/Outpatient visit; 5=Hospitalization; 6=Referral for treatment

Outcome: 1=Resolved; 2=Recovered with sequelae; 3=Ongoing; 4=Required treatment; 5=Unknown

Programmer's Note: If "Were any AEs reported?" checkbox=No, then display "None Reported" in the Adverse Event column and SOC/PT column. If an AE started and stopped the same day, the duration is 1 day.

Listing 29: Serious Adverse Events

Subject ID	Treatment Group	SAE Verbatim S: SOC P: PT	Start Date/ Day	Stop Date/ Day	SAE Category	Severity	Relationship
XXX	Oxytocin	Verbatim	mm/dd/yyyy	mm/dd/yyyy	Death	1	1
	Placebo	S: XXX	Xx	Xx	Life-threatening	2	2
		P: XX			Hospitalization	3	3
					Disability	4	4
					Congenital Anomaly/Birth Defect	5	5
					Required Intervention to Prevent Permanent Impairment / Damage		
					Other		

Subject ID No.	SAE	Continued Study Participation	Study Drug Start Date	Date of last administration of study drug prior to SAE	SAE Abated after study drug stopped?	Continued study drug Administration	SAE reappeared after rechallenge?	Outcome
XXX	Verbatim	Yes	mm/dd/yyyy	mm/dd/yyyy	Yes	Yes	Yes	1
		No			No	No	No	2
					n/a		n/a	3

Severity: 1=Mild; 2=Moderate; 3=Severe; 4=Potentially Life-threatening. Relationship: 1= Unrelated; 2=Unlikely; 3=Possibly; 4=Probably; 5=Definitely

Outcome: 1=Recovered/Resolved; 2=Recovering/Resolving; 3=Not Recovered/Not Resolved; 4=Recovered/Resolved With Sequelae; 5=Fatal (Date of Death)

Listing 30: Columbia-Suicide Severity Scale

				Response to Question:												
Subjec t ID	Treatment Group	Visit Date	Study Week	Q1	Q2	Q3	Q4	Q5	Q6	Q7	Q8	Q9	Q10	Q11	Q12	Q13
XXX	Oxytocin	mm/dd/yyyy	1, 2, 5	Yes	Yes	Yes	Yes	Yes	Yes	Type 1	1	1	0	0	0	Yes
	Placebo		9, 13	No	No	No	No	No	No	Type 2	2	2	1	1	1	No
										Type 3	3	3	2	2	2	
										Type 4	4	4	3	3	3	
										Type 5	5	5	4	4	4	
													5	5	5	

Suicide Ideation

- 1. Have you wished you were dead or wished you could go to sleep and not wake up?
- 2. Have you actually had any thoughts of killing yourself?
- 3. Have you been thinking about how you might do this?
- 4. Have you had these thoughts and had some intention of acting on them?
- 5. Have you started to work out or worked out the details of how to kill yourself?
- 6. Do you intend to carry out this plan?

Intensity of Ideation

- 7. The following features should be rated with respect to the most severe type of ideation (i.e. 1-5 with 1 being the least severe and 5 being the most severe)
- 8. How many times have you had these thoughts?1=Less than once a week; 2=Once a week; 3=2-5 times a week; 4=Daily or almost; 5=Many times each day
- 9. When you have the thoughts, how long do they last? 1=Fleeting-few seconds or minutes; 2=Less than 1 hr-some of the time; 3=1-4 hrs/a lot of time; 4=4-8 hrs/most of day; 5=More than 8 hours/persistent or continuous
- 10. Could/can you stop thinking about killing yourself or wanting to die if you want to? 1=Easily; 2=Little Difficulty; 3=Some Difficulty; 4=Lot of Difficulty; 5=Unable to control; 0=Does not attempt to control
- 11. Are there things that stop you from wanting to die or acting on thoughts of committing suicide? 1=Definite deterrents; 2=Probably Deterrents; 3=Uncertain Deterrents; 4=Unlikely Deterrents; 5=No Deterrents; 0=Does not apply
- 12. What sort of reasons did you have for thinking about wanting to die or killing yourself? Was it to end pain or stop the way you were feeling or to get attention, revenge or reaction from others 1=Completely to get attention or revenge or reaction; 2=Mostly to get attention or revenge or reaction; 3=Equally to get attention or revenge or reaction and stop pain; 4=Mostly to stop pain; 5=Completely to stop pain; 0=Does not apply

Suicidal Behavior

- 13. Have you made a suicide attempt?
- 14. Number of attempts
- 15. Has the subject engaged in non-suicidal self-injurious behavior?
- 16. Has there been a time when you started to do something to end your life but someone or something stopped you before actually did anything?
- 17. Number interrupted
- 18. Has there been a time when you stared to do something to try to end your life but you stopped yourself before you actually did anything?
- 19. Number aborted
- 20. Have you taken any step towards making a suicide attempt or preparing to kill yourself?
- 21. Suicidal behavior was present during the assessment period
- 22. Completed suicide?
- 23. Actual Lethality/Medical Damage; 0=No physical damage; 1=Minor physical damage; 2=Moderate physical Damage; 3=Moderately severe physical damage; 4=Severe physical damage; 5=Death
- 24. Potential Lethality; 0=Behavior not likely to result in injury; 1=Behavior likely to result in injury, but not death; 2=Behavior likely to result in death

Listing 31: BPAQ Scores

				Scores									
Subject ID	Treatment Group	Week	Physical Aggression	Verbal Aggression	Hostility	Anger							
XXX	Oxytocin	XX	XXX	XXX	XXX	XXX							
	Placebo												

Listing 32: Blood Chemistries

Subject ID	Treatment Group	Visit Date	Test Name	Result	Units	Flag	Evaluation
xxxx	Oxytocin	mm/dd/yyyy	Creatinine	X.XX	mg/dL	H (high)	WNL
	Placebo		Total Bilirubin	XXX	mg/dL	L (low)	Abnormal, NCS
			ALT	XX.X	U/L		Abnormal, CS
			AST	X.XX	U/L		
			sodium	XX.X	U/L		
			Potassium				

Listing 33: Pregnancy Test/Birth Control Data

Subject ID	Treatment Group	Pregnancy Test Performed?	Pregnancy Test Date	Pregnancy Result	Methods of birth control
XXX	Oxytocin	Not Done	mm/dd/yyyy	Negative	Oral Contraceptive
	Placebo			Positive	Contraceptive Sponge
					Contraceptive Skin Patch
					Double Barrier
					Intrauterine
					Etonogestrel implant
					Medroxyprogesterone
					Complete Abstinence
					Hormonal Vaginal contraceptive Ring
					Surgically Sterile
					Postmenopausal
					Partner surgically Sterile
					Other: xxxxxxxxxxxxxx

Programming note: Only indicate birth control methods that were indicated as Yes

Listing 34: **Blood Alcohol Concentration**

Subject ID	Treatment Group	Visit Date	Study Week	BAC Performed	Time of BAC	BAC %
XXX	Oxytocin	mm/dd/yyyy	Screen	Done	hh:mm	x.xxx
	Placebo		1, 2, 3	Not Done		
			4, 6, 8			
			10, 13			

Listing 35: Urine Drug Screen

Subject ID	Treatment Group	Visit Date	Study Week	AMP a,b	Benzos	Barb	Coc	Bup	EGT	MDMA	Meth	Methadone	Opioids	Оху	THC
XXX	Oxytocin	mm/dd/yyyy	Screen	P	P	P	P	P	P	P	P	P	P	P	P
	Placebo		1, 2, 3	N	N	N	N	N	N	N	N	N	N	N	N
			4, 6, 8												
			10, 13												

 ^a P=positive; N=negative
 ^b AMP=amphetamine, Benzos=benzodiazepines, Coc=cocaine, Meth=methamphetamine, Oxy=oxycodone, Bup=buprenorphine, Barb=barbiturates

Listing 36: Vital Signs and Body Weights

[figure not shown]
Subject ID	Treatment Group	Visit Date	Study Week	Weight (Kg)	Heart Rate (beats/min)	Systolic Pressure (mmHg)	Diastolic Pressure (mmHg)
		/11/	G :				
XXX	Oxytocin	mm/dd/yyyy	Screening	XXX	XXX	XXX	XXX
	Placebo		4				
			8				
			12, 16, 20				
			24, 26, 27				

Listing 37: Prior and Concomitant Medications

Subject ID	Treatment Group	Prior Med?	Verbatim Med	Indication	Route	Frequency	Dose	Start Date	Stop Date	Continuing?
XXX	Oxytocin	Yes	XXX	xxxxxx	XXXXXX	XXXXXX	XXXXXX	dd/mmm/yyyy	dd/mmm/yyyy	Yes
xxx	Placebo	No	XXX							No

